### **g) Objectives:**

The aim of this proposed project will be to compare the mood- and cognitive-enhancing effects of 8 sessions of prefrontal EEG and fNIRS neurofeedback training programmes in older adults with subclinical depression and anxiety through a randomised controlled trial. We planned to compare EEG and fNIRS neurofeedback because in principle they act on two different aspects of brain function. Because electrical activity and hemodynamic activity in the brain have a non-perfect relationship (Shibasaki, 2008), the two neurofeedback methods may yield varying effects. In addition, we chose EEG and fNIRS because they are the only two existing neuroimaging methods that allow for real-time human-computer interactions conducted through a wearable system. The findings will provide crucial knowledge about whether prefrontal neurofeedback training can reduce the risks of affective disorders and accelerated cognitive decline in old age (Steenland et al., 2012; Richard et al., 2013).

Three objectives are set, as follows:

- 1) To elucidate whether EEG and fNIRS neurofeedback training programmes improve the mental health of older adults with subclinical depression and anxiety;
- 2) To determine whether EEG and fNIRS neurofeedback training programmes enhance the frontal cognitive functions of older adults with subclinical depression and anxiety; and
- 3) To compare the relative effectiveness of these two programmes based on different neural mechanisms in enhancing the mental health and cognitive functions of older adults with subclinical depression and anxiety.

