The proposed sample size was determined based on randomised controlled trials on neurofeedback training for mood/anxiety disorders, which collectively reported a weighted mean Cohen's  $f$  of 0.59 for the group  $\times$  time interaction on the scores for depression, anxiety, and/or post-traumatic stress  $[(0.37 \times 90 + 0.88 \times 24 + 0.89 \times 44 + 0.63 \times 18)/(90 + 24 + 44 + 18)]$  (Lee et al., 2019; van der Kolk et al., 2016; Wang et al., 2019; Zilverstand et al., 2015). Accordingly, a power analysis (G\*Power v3.1.9.4) indicated that 14 participants per group will be required to detect any significant differences between the three groups based on a power of 0.80 and an alpha level of 0.017 (three outcome measures per data type). We expect a smaller effect size for subclinical populations and a loss of participant data due to dropouts and unusable data. As such, **we will recruit 30 individuals per group.**

**Study Procedures:** Potential participants will first be subjected to a screening evaluation to assess eligibility. Eligible individuals will be invited to PolyU for assessment and training. The training will comprise 8 60-min sessions conducted within 4 weeks. Each session will include 25-min effective training time, for a total training time of 250 min, in keeping with recent recommendations (Kohl et al., 2020). In addition, the participants will undertake several experimental tasks under simultaneous EEG–fNIRS recording and complete several questionnaires at three time points, as described in the 'Neurophysiological Assessment' section. Multiple studies have demonstrated that EEG, fNIRS, and neurofeedback training can be applied to older adults over 70, and even to individuals with dementia (Laborda-Sánchez & Cansino, 2021; Trambaiolli et al., 2021; Yeung & Chan, 2021). Therefore, we expect that older adults who are screened for dementia by the HK-MoCA will be able to follow both the assessment and training protocols.

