Each assessment task (eyes open, Emotional Stroop, *n*-back) proposed for this research will comprise a difficult and an easy condition. The eyes open test is used to let the machine measure the activation baseline when the participants open their eyes (Barry & De Blasio, 2017). It requires participants to maintain their eyes open for 3 minutes. The Emotional Stroop task is used to assess inhibitory control (Imbir et al., 2022). Participants are shown photos of different emotions with unrelated traditional Chinese emotion names. They are asked to name the photos by emotion. It requires participants to inhibit their emotions lead by the wordings and react to the content of the photo. Differences in accuracy and mean RT and changes in the prefrontal HbO concentration and theta power between the two conditions will be the dependent variables. The *n*-back task is used to assess working memory (Yeung et al., 2016b, 2019b). During the task, participants are shown a sequence of digits and asked to judge via button press whether the digit they are seeing is zero (0-back; easy) or the same as the digit they saw two trials before (2-back; difficult). Differences in accuracy and mean reaction time (RT) and changes in the prefrontal HbO concentration and theta power between the two conditions will be the dependent variables.

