**Data Analysis:** In this project, the primary outcome measures are mood and anxiety measures (i.e., DASS-21 and HADS scores), and the secondary outcome measures are task performance and PFC measures, as well as other mental health measures. The outcome measures will be analysed according to the CRED-nf checklist (Ros et al., 2020). Linear mixed models with group (sham, EEG, fNIRS), time (baseline, post, follow-up), and condition (easy, difficult) as the fixed factors; age and education years as covariates; and the subject as a random factor will be used to analyse the behavioural, fNIRS, and EEG data. We expect that participants in the two real neurofeedback training groups will demonstrate significant improvements in mental health, cognitive function, and frontal lobe function at the post and follow-up assessments relative to the sham group participants. In addition, we will evaluate differences in pre–post changes in mental health and cognitive functions between the two real training groups to address Objective 3. Moreover, we will examine the correlation between baseline cognitive and PFC functioning levels and the pre-post changes in DASS-21 scores to elucidate individual differences in the treatment response for each neurofeedback group.

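### Task outcomes are defined as differences between conditions, but the mixed model keeps condition as a factor with only subject random; with one row per condition, the test of that difference uses too large an error

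*Combined protocol and SAP*

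**What the plan says.** All of this is in the combined protocol and SAP.

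- **Outcome definition** (section h, Neurophysiological Assessment). The dependent variables for the Emotional Stroop are "Differences in accuracy and mean RT and changes in the prefrontal HbO concentration and theta power between the two conditions". The n-back paragraph uses the same construction: "Differences in accuracy and mean reaction time (RT) and changes in the prefrontal HbO concentration", again with theta power and again between the two conditions. This gives one value per person per visit for each measure.
- **Model** (section h, Data Analysis). The plan specifies "Linear mixed models with group (sham, EEG, fNIRS), time (baseline, post, follow-up), and condition (easy, difficult) as the fixed factors". Age and years of education are covariates, and "the subject as a random factor will be used to analyse the behavioural, fNIRS, and EEG data".
- **Status.** Data Analysis states that "the secondary outcome measures are task performance and PFC measures", alongside other mental health measures. Objective 2 in section g depends on them: "To determine whether EEG and fNIRS neurofeedback training programmes enhance the frontal cognitive functions of older adults".

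The plan names no interaction as the test of interest, no random term beyond subject and no residual covariance. Appendix I covers online signal processing only and does not settle the matter.

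**The concern.** Once the difference has been taken, condition cannot be a factor. Condition can be a factor only if each condition has its own row, and then the dependent variable is no longer the difference that the assessment section defines. An analyst must choose between the two layouts, and the plan does not say which.

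The choice matters. With condition-level rows, the effect of training on the easy–difficult difference is the group × time × condition interaction. A model whose only random term is a subject intercept treats all remaining within-person variation as one homogeneous error. If people drift in overall level between visits, or differ in their own easy–difficult gap, that variation enters the error for the three-way test, where it does not belong. A real training effect on frontal cognition or prefrontal activity could then be missed. The group × time test, averaged over conditions, shares the same pooled error and can err in either direction. With no test named, the choice between the two could also be made after the data are seen.

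**Working it through.** **The plan's own figure.** The sample-size paragraph's weighted effect is (0.37×90 + 0.88×24 + 0.89×44 + 0.63×18)/176 = 104.92/176 = 0.596 (stated as 0.59). For a three-group omnibus F test with f = 0.59 and "an alpha level of 0.017 (three outcome measures per data type"), 14 per group gives power 0.823 and 13 gives 0.784. So 14 is reproduced. It does not involve condition and is not affected by this point.

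**Inputs.** From the documents: 3 groups of 30 (90 people), 3 visits, 2 conditions, alpha 0.017 for the sample size. Assumed: one row per person, visit and condition; balanced data; subject-by-time variance t, subject-by-condition variance c and residual variance e. The documents give none of these variances, so the results are shown over a range of t/e and c/e. Alpha 0.05 is shown beside 0.017.

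**Correct errors.** There are 90 − 3 = 87 between-subject degrees of freedom within groups.

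| Test | Correct error | Error df |
|---|---|---|
| group × time | e + 2t | 87×2 = 174 |
| group × condition | e + 3c | 87×1 = 87 |
| group × time × condition | e | 87×2 = 174 |

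**Error with a subject intercept only.** The three strata are pooled on 435 df:

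[174(e + 2t) + 87(e + 3c) + 174e]/435 = e + 0.8t + 0.6c

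- For the three-way test this exceeds e whenever t or c is above zero.
- For group × time, compare e + 2t with e + 0.8t + 0.6c. The pooled error is too small if 1.2t > 0.6c, that is t > c/2, and too large if t < c/2.

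**Size of the effect.** The effect is set to give 80% power with the matching error (4 and 174 df; noncentrality 12.26 at alpha 0.05 and 15.74 at 0.017). The mean squares are then drawn 1,000,000 times per case. The 1-df column is a single contrast calibrated in the same way.

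| t/e, c/e | Pooled / correct error | Three-way power (type I), α 0.05 | 1-df power, α 0.05 | Group × time type I, α 0.05 | Three-way power, α 0.017 | Group × time type I, α 0.017 |
|---|---|---|---|---|---|---|
| 0, 0 | 1.00 | 81% (5.0%) | 80% | 5.0% | 81% | 1.7% |
| 0, 0.14 | 1.08 | 77% (3.6%) | 78% | 3.6% | 77% | 1.1% |
| 0.25, 0 | 1.20 | 71% (2.3%) | 75% | 10.7% | 70% | 4.7% |
| 0.25, 0.25 | 1.35 | 63% (1.3%) | 70% | 7.4% | 61% | 2.9% |
| 0.33, 0.33 | 1.46 | 57% (0.8%) | 67% | 7.9% | 55% | 3.1% |
| 1.5, 0.5 | 2.50 | 16% (0.01%) | 39% | 20.3% | 12% | 10.9% |

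The three-way standard error is too large by the square root of the ratio, so 1.04 to 1.58 times from the second row to the last. Very small components do no harm: power is 80.4% at (0.01, 0), 80.1% at (0, 0.02) and 79.4% at (0.02, 0.02).

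**Missing data.** The plan expects "a loss of participant data due to dropouts and unusable data" but gives no rate. Row-level REML fits were run under assumed rates (12,000 replicates for type I error, 4,000 for power, alpha 0.05), comparing the written model's three-way test with group × time on the difference score.

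| Case | Type I: written v difference | Power: written v difference |
|---|---|---|
| (0.25, 0.25), balanced | 1.1% v 4.9% | 63% v 79% |
| (0.25, 0.25), 10%/20% of visits missing at post/follow-up | 1.4% v 5.2% | 62% v 78% |
| (0.25, 0.25), 15%/30% missing | 1.5% v 5.2% | 58% v 75% |
| (1.5, 0.5), 10%/20% missing | 0.0% v 4.9% | 15% v 76% |

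**The case against.** The strongest reply is that the two sections can share one estimand. The assessment section names the contrast, and the Data Analysis paragraph names a model in which the three-way interaction estimates it. On that reading the fault is loose wording. This is fair as far as it goes, but the plan does not name that interaction, and the only random term it writes gives the interaction the wrong error.

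Second, the harm is conditional. It needs condition-level rows, one row per cell, a subject intercept only, and t or c above zero. If difference scores are analysed, or if subject as a random factor was meant to cover further random terms, the problem disappears. With trial-level or channel-level rows the error could instead be too small. All of this stands, and it is why the plan needs to state the layout.

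Third, the omnibus figures overstate the loss for the comparisons that Data Analysis describes, which are each real group against sham and the two real groups against each other. This also stands. The 1-df losses are smaller (78% down to 39%, against 77% down to 16%) but run in the same direction. The omnibus test remains relevant because the sample-size paragraph is built on a three-group test.

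Fourth, nothing in the documents supports any particular variance ratio, least of all (1.5, 0.5). Correct: the table is a range and not a forecast.

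Finally, the repair is not perfect. A subject intercept on the difference scores still assumes equal correlation between visits. With an autoregressive visit correlation of 0.5 in the residual and 10%/20% of visits missing, its type I error was 5.6%. That is a small departure beside the written model's 0.3% in the same case.

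**Conclusion.** The concern holds. The outcome definition and the model are not reconciled anywhere in the document. The model followed literally, with one row per cell and a subject intercept only, tests the stated outcome against e + 0.8t + 0.6c when the correct error is e. The direction is certain whenever t or c exceeds zero. The size is not known, because it rests on assumed variance ratios. Moderate values (0.25 to 0.33 for both) cost about 17 to 23 points of omnibus power at alpha 0.05, or 10 to 13 points for a single contrast. In those cases group × time rejects a true null 7.4% to 7.9% of the time. If both components are zero, the written model is valid.

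The effect is confined to the secondary task and prefrontal outcomes, and so to Objective 2 and the cognitive part of Objective 3. DASS-21 and HADS have no condition factor, and the sample size is unchanged. This should be fixed before the analysis is finalised, but it does not threaten the primary result.

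**What to change.** In Data Analysis, choose one layout in advance for the task, HbO and theta outcomes:

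1. Analyse one easy–difficult difference per person per visit, with group, time, group × time, the planned covariates and a subject random effect, and no condition term. The test for Objective 2 is group × time.
2. Keep both conditions as rows, add subject-by-time and subject-by-condition random effects (or an equivalent covariance structure), and name group × time × condition as the test.

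In balanced data the two give the same test, provided no variance estimate falls on zero. The first is simpler and matches the outcome definition already written. Whichever is chosen, state the row unit and the residual covariance.

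The cost is a few lines of text, with the same data, visits, sample size and software. Error degrees of freedom fall from 435 to 174, which costs about 0.8 points of power at alpha 0.05 if t and c are truly zero.

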### **h) Research Plan and Methodology:**

**Design:** This proposed project has been designed in accordance with current consensus on the reporting and experimental design of clinical and cognitive-behavioural neurofeedback studies (CRED-nf; Ros et al., 2020). The participants will be randomly and equally assigned to one of three neurofeedback training groups: (1) sham, (2) EEG, and (3) fNIRS. Each participant will

complete a neurophysiological assessment (1) before, (2) immediately after, and (3) 1 month after the intervention (see Appendix I).

**Participants:** Ninety older adults without dementia will be recruited via advertisements at PolyU and community centres for older adults. The inclusion criteria will be as follows: (i) age of 60–79 years; (ii) right-handedness as assessed using the short form of the Edinburgh Handedness Inventory (Veale, 2014); (iii) a moderate or higher score on at least one of the depression and anxiety subscales (but not necessarily both) of the Depression Anxiety Stress Scale-21 (DASS-21), which has been shown to yield reliable and valid scores (Gomez, Summers, Summers, Wolf, & Summers, 2014; Norton, 2007); (iv) no history of neurological or psychiatric disorder; (v) no history of traumatic brain injury requiring hospitalisation; (vi) not currently using psychotropic medication; (vii) ability to read Traditional Chinese text; (viii) normal or corrected-to-normal vision; and (ix) a score of at least 19 on the Hong Kong Montreal Cognitive Assessment (HK-MoCA; Wong et al., 2009).

The inclusion criteria that we planned to use were based on those employed by prefrontal neurofeedback studies in mood or anxiety disorders (e.g., Kimmig et al., 2019; Peeters et al., 2014). Conventionally, participants are selected based on a certain threshold of depressive or anxiety symptoms, or the clinical diagnosis; neither cognitive nor brain dysfunction constitutes an inclusion criterion. Nevertheless, since variation in cognitive and PFC functioning levels may affect the treatment response, subsequent analyses will consider baseline cognitive and PFC functioning levels.

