**Neurophysiological Assessment:** A 1.5-h neurophysiological assessment will be administered at each of three time points (pre, post, and 1-month follow-up) to evaluate the effects of neurofeedback training. The participants will complete the DASS-21 (Chinese version) to measure their depressive and anxiety symptoms over the last week (Gomez et al., 2014; Norton, 2007); the Hospital Anxiety and Depression Scale (HADS; Chinese version) to measure their signs of anxiousness and depression during the previous week (Flint & Rifat, 2002); the Pittsburgh Sleep Quality Index to measure their sleep quality over the last month (Buysse et al., 1989); the Satisfaction with Life Scale (Chinese version) to quantify their general life satisfaction (Wu & Yao, 2006); and Lawton Instrumental Activities of Daily Living Scale (IADL; Chinese version) to assess independent living skills (Tong & Man, 2002). The participants will also complete three computerised tasks to assess different components of frontal cognitive function (see below) under simultaneous EEG–fNIRS measurements, using the same setup described for neurofeedback training. At the first visit, the participants will also complete the HK-MoCA to screen for dementia (Wong et al., 2009). Immediately after the intervention, they will be asked whether they know their treatment group assignment to check the strength of blinding.

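### A single subject random factor forces equal variance and correlation on the three visits; if correlation falls with time, the 1-month comparison with sham has too small a standard error

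*Combined protocol and SAP*

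**What the plan says.** All the relevant text is in section h, Research Plan and Methodology.

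- **Model (Data Analysis).** The fixed part is group, "time (baseline, post, follow-up), and condition (easy, difficult) as the fixed factors", with age and years of education as covariates. The random part is "and the subject as a random factor will be used to analyse the behavioural, fNIRS, and EEG data". The text names no random slope, subject-by-visit term, residual covariance, degrees-of-freedom method or robust variance.
- **Primary outcomes (Data Analysis).** "the primary outcome measures are mood and anxiety measures (i.e., DASS-21 and HADS scores". Each gives one score per visit. No other model is named for them.
- **Contrasts (Data Analysis).** The real training groups are expected to improve "at the post and follow-up assessments relative to the sham group participants". EEG and fNIRS (Objective 3) are compared on change from pre to post only.
- **Visits (Design; Study Procedures).** Participants "complete a neurophysiological assessment (1) before, (2) immediately after, and (3) 1 month after the intervention", and "The training will comprise 8 60-min sessions conducted within 4 weeks". The gaps are therefore up to 4 weeks and then 1 month, and baseline to follow-up is about twice either one.

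**The concern.** A mixed model whose only random term is a subject intercept assumes that every pair of visits is equally correlated and every visit equally variable. It then uses one pooled within-subject error for every change contrast. Scores taken about two months apart are commonly less alike than scores taken one month apart. If that holds here, the pooled error understates the variance of change from baseline to follow-up and may overstate the variance of change from baseline to post.

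The 1-month comparison with sham is the trial's evidence of lasting benefit, and the Introduction itself faults earlier work for lacking randomised trials with follow-up. Intervals that are too narrow there raise the false-positive risk. A pooled error that is too large at post costs power for the immediate comparison with sham and for EEG versus fNIRS.

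**Working it through.** **The plan's own figure.** The plan gives no variance or correlation to reproduce. Its one computed figure, 14 per group, does reproduce. With f = 0.59, λ = 0.59² × 42 = 14.62, and an F test on 2 and 39 degrees of freedom at alpha 0.017 has power 0.823. That figure does not depend on this point.

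**Inputs from the documents.** Three visits, three equal arms of 30, subject as the only random term. Alpha 0.017 appears only in the sample-size paragraph, so 5% and 1.7% are both shown. **Assumed:** every SD and correlation below.

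**Formula.** For visits i and j, Var(d) = σᵢ² + σⱼ² − 2ρσᵢσⱼ. With complete balanced data, the random-intercept residual variance is the mean of Var(d)/2 over the three pairs. Let r = Var(d for the contrast) / mean Var(d). Then model SE / true SE = 1/√r, and the large-sample error is 2[1 − Φ(z/√r)], with z = 1.960 (5%) or 2.387 (1.7%).

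**Worked example.** Take unit SDs and correlations 0.6 (pre–post), 0.5 (pre–follow-up) and 0.7 (post–follow-up). Var(d) = 0.8, 1.0 and 0.6, with mean 0.8.

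- 1 month: r = 1.0/0.8 = 1.25, SE ratio 0.89, error 2[1 − Φ(1.960/1.118)] = 8.0%.
- Post: r = 0.8/0.8 = 1, error 5%.

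**Range.** Results are from 20,000 simulated trials per row with no effect, 30 per arm, complete data and no covariates. The row marked * uses the formula. Each cell gives the SE ratio, then the error at nominal 5% / 1.7%, for one pairwise group contrast.

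| Assumed covariance (pre–post / pre–follow-up / post–follow-up) | 1 month | Post |
|---|---|---|
| Equal, 0.6 | 1.00; 4.9% / 1.7% | 1.00; 5.1% / 1.7% |
| 0.6 / 0.55 / 0.6* | 0.96; 5.9% / 2.2% | 1.02; 4.5% / 1.5% |
| 0.6 / 0.5 / 0.7 | 0.89; 8.1% / 3.6% | 1.00; 4.9% / 1.8% |
| AR(1), lag-1 0.5 | 0.88; 8.4% / 3.5% | 1.08; 3.4% / 1.0% |
| AR(1), lag-1 0.7 | 0.85; 9.6% / 4.2% | 1.11; 3.2% / 0.9% |
| AR(1), lag-1 0.8 | 0.84; 10.2% / 4.4% | 1.13; 2.8% / 0.7% |
| Baseline SD 0.7 of later SDs, all 0.6 | 1.04; 4.4% / 1.5% | 1.04; 4.3% / 1.5% |
| Baseline SD 0.7 of later SDs, 0.4 / 0.4 / 0.7 | 0.94; 6.5% / 2.6% | 0.94; 6.8% / 2.7% |

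**Adding entry selection on DASS-21.** Assume normal scores, a depression–anxiety correlation of 0.6 and 20% above the cut on each subscale, with selection on either. The correlations are those before selection. The formula at nominal 5% gives:

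- 0.6/0.55/0.6: 5.5% at 1 month, 4.3% at post.
- 0.6/0.5/0.7: 7.4% and 4.9%.
- 0.5/0.45/0.7: 7.1% and 6.0%.
- 0.6/0.55/0.8: 8.0% and 6.5%.
- AR(1) with lag-1 0.7: 8.9% and 3.1%.
- All 0.6: 4.6–4.7% at both visits.

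Simulation with this selection, over correlations of 0.5–0.6, 0.45–0.55 and 0.70–0.80, gave 7.1–7.8% at 1 month and 4.9–7.8% at post.

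**Omnibus test and remedy.** Over the simulated scenarios, which also included SDs rising or falling over time, the omnibus group-by-time test had error 5.1–6.4% at nominal 5% and 1.7–2.7% at nominal 1.7%. Contrasts with visit-specific variance, equivalent here to an unstructured covariance, held 4.7–5.3% and 1.7–1.9% at both visits.

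**The case against.** - **The plan leaves the covariance unspecified; it does not state a wrong one.** This is fair. Subject as a random factor can be combined with a structured residual, so equal correlation is the ordinary reading and not a quoted assumption. But run as written, the model pools the error, and the remedy is the same on either reading.
- **The model sentence may not cover the questionnaires.** It refers to behavioural, fNIRS and EEG data and includes a condition factor that DASS-21 and HADS lack. Its reach to the primary outcomes is therefore inferred. If it does not reach them, they have no stated model, and the text still needs changing.
- **The effect comes from assumed correlations.** This stands. With mild decay (0.6/0.55/0.6) the 1-month error is only 5.5–5.9%, and with equal correlations there is no excess.
- **A reader might infer false positives at both visits.** The calculations do not support that. Under plain decay with roughly equal spacing the post contrast is conservative, and it is inflated only under some other patterns.
- **A reader might blame the entry criterion**, "a moderate or higher score on at least one of the depression and anxiety subscales (but not necessarily both", for narrowing the baseline spread. Taken alone, that gives error slightly below nominal. It also concerns DASS-21 directly; HADS is not a selection variable.
- **A reader might take 0.017 as the analysis alpha.** It is a planning figure; the Data Analysis paragraph sets no level.

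**Conclusion.** The point holds in a limited form and is worth correcting before unblinding. As ordinarily read, the model imposes equal variance and correlation on three visits whose spacing gives reason to doubt it.

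If correlation falls with time, the standard error for baseline to 1 month is too small: by about 4% under mild decay and 11–16% under the stronger patterns. The corresponding two-sided error is about 5.5–10% at nominal 5% and about 2–4.5% at 1.7%. The direction at post is not fixed: about 3% (lost power, including for Objective 3), nominal, or about 6–8%.

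The documents do not establish that inflation is likely, because they report no SDs or correlations. The calculations also assume complete data and no covariates; dropout could change the sizes.

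**What to change.** In the Data Analysis paragraph, for outcomes with one value per visit (DASS-21, HADS, sleep quality, life satisfaction, IADL and task difference scores), replace the subject random factor with wording such as:

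*Repeated-measures linear mixed model with group, time and group-by-time, adjusted for age and years of education, with unstructured covariance across the three visits, fitted by REML with Kenward-Roger degrees of freedom. Each active group is contrasted with sham at post and at follow-up. If the model does not converge, a heterogeneous Toeplitz covariance or a robust (sandwich) variance will be used.*

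The EEG versus fNIRS contrast on pre–post change comes from the same model. Task data analysed with both condition rows kept need their own random structure, which this wording does not cover.

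The cost is one passage of text and no new data. There are six covariance parameters (three variances, three covariances) instead of two. Error degrees of freedom are about 90 − 3 = 87 instead of (90 − 3) × 2 = 174. Both are negligible with 90 participants.

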al., 2008). PFC dysfunction may cause the amygdala to become overactivated and dysregulated, resulting in mood and anxiety symptoms. This prefrontal–subcortical model has received extensive support from neuropsychological and neuroimaging studies of mood and anxiety disorders (Grahek et al., 2019; Mochcovitch et al., 2014; Snyder, 2013; Snyder et al., 2015). **Our and others' work also supports the utility of this model for studying subclinical depression and anxiety (Mathersul et al., 2008; Szymkowicz et al., 2019; Yeung et al., 2021a, b).** For example, our recent study showed similar negative relationships between PFC functioning and symptoms of depression and anxiety in non-psychiatric older adults (Yeung et al., 2021a).

In humans, emotion is addressed by the frontal asymmetry model, which posits that the left and right frontal lobes mediate positive emotion/approach behaviour and negative emotion/withdrawal behaviour, respectively. In keeping with this model, converging evidence indicates that mood and anxiety symptoms are primarily associated with reduced left frontal activity and increased right frontal activity, respectively, and both are related to a reduction in left-asymmetric frontal activity in resting and task states in both clinical and general populations (Adolph & Margraf, 2017; Bruder et al., 2017; Mathersul et al., 2008). **Therefore, improving PFC function, particularly restoring frontal asymmetry, represents a promising trajectory for enhancing the mental health and cognitive function of older adults with subclinical depression and anxiety.** To date, this has remained an unexplored area in neuroscience research on ageing.

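### Arm contrasts leave the baseline outcome score out as a covariate, which costs precision, and treatment response is read from per-group correlations that no test compares

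*Combined protocol and SAP*

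**What the plan says.** All of this is in section h. The Data Analysis paragraph specifies linear mixed models with group, time (baseline, post, follow-up) and condition as fixed factors, with "age and education years as covariates; and the subject as a random factor". Baseline is therefore one of the responses. No baseline outcome score is a covariate, and no common baseline mean across arms is imposed. Objective 3 is addressed by a contrast of changes: "we will evaluate differences in pre–post changes in mental health and cognitive functions between the two real training groups".

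For response to treatment the same paragraph says "we will examine the correlation between baseline cognitive and PFC functioning levels and the pre-post changes in DASS-21 scores", and gives the purpose as "to elucidate individual differences in the treatment response for each neurofeedback group". The Participants text gives the motive: "since variation in cognitive and PFC functioning levels may affect the treatment response, subsequent analyses will consider baseline cognitive and PFC functioning levels". It adds no model term and no test. Entry requires "a moderate or higher score on at least one of the depression and anxiety subscales" of the DASS-21, so participants are selected on the scale that later supplies the change score.

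**The concern.** There are two separate issues.

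**Precision.** A random-intercept model with free baseline means in each arm yields, on complete data, a group-by-time contrast equal to the difference in mean change. Age and education as main effects are constant within a participant and drop out of it. Unless the regression of post on baseline has slope 1, a contrast adjusted for the baseline score has smaller variance. With 30 per arm, the intervals for the active-versus-sham and EEG-versus-fNIRS contrasts would be wider than the collected data require.

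**Treatment response.** A correlation between a baseline marker and symptom change within one arm mixes three things: a different effect of training, a different course without training, and regression to the mean. Only comparison with sham separates the first from the others, and the plan states no such comparison. The link between marker and severity is the plan's own premise: section f cites earlier work showing "similar negative relationships between PFC functioning and symptoms of depression and anxiety in non-psychiatric older adults". A correlation significant in one arm and not in another could then be reported as a response marker without support.

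**Working it through.** **Context: the plan's own sample size.** A one-way F test of three groups with f = 0.59 and alpha = 0.017 at n = 14 per group has noncentrality 0.59² × 42 = 14.6 and power 0.823. The stated 14 per group is reproduced. It takes no credit for baseline adjustment and is not in dispute here.

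**Part (a), precision**

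1. *Equivalence.* In one simulated data set of 3 × 30 participants and 3 visits, the mixed-model group-by-time estimate was 0.482 (SE 0.235), with or without age and education. The difference in mean change was also 0.482.

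2. *Formula.* Let r be the pre-post correlation before selection, with equal variances scaled to 1, and V the baseline variance left after the entry rule. Per arm:
   - change score: (1 − r)²V + (1 − r²)
   - baseline-adjusted: 1 − r²
   - ratio, adjusted to change: (1 + r) / [(1 + r) + (1 − r)V]

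3. *Without selection* (V = 1) the ratio is (1 + r)/2: 0.65 at r = 0.3 and 0.85 at r = 0.7. In 20,000 simulated trials per value of r, both estimators were centred on the true value of zero.

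4. *With the entry rule.* The documents give no correlations or cut-off distribution, so these are assumptions: two subscales correlated 0.5 or 0.7; entry if either exceeds z = 0.84 or 1.28; HADS correlated 0.6 or 0.8 with the subscale; r = 0.3 to 0.7. Simulation gives V of about 0.46 to 0.69 for a DASS-21 subscale.
   - Low end: 1.3 / (1.3 + 0.7 × 0.69) = 0.73.
   - High end: 1.7 / (1.7 + 0.3 × 0.46) = 0.925; direct simulation gave 0.927.

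| Outcome | Variance ratio | 30 per arm worth |
|---|---|---|
| DASS-21 subscale | 0.73–0.93 | 32–41 |
| HADS | 0.67–0.90 | 33–45 |

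   Selection shrinks the baseline variance, so the gain is smaller than in the unselected case.

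5. *Power* (noncentral t, 30 per arm). A contrast with 60% power at ratio 1 has 74% at ratio 0.73 and 63% at 0.93 with alpha 0.05. With the plan's 0.017 the figures are 76% and 64%.

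**Part (b), correlations, n = 30 per group**

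1. *With no treatment effect.* Assume the marker correlates −0.3 with baseline symptoms before selection. Regression to the mean alone then gives r(marker, change) of +0.06 to +0.13. If the marker also predicts later symptoms (assumed partial r of −0.3), it becomes −0.12 to −0.23.

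2. *Separate significance.* |r| must exceed 0.361 for p < 0.05. If the true r is 0.3 in every group, each has power 0.363. Exactly one of two groups is significant with probability 2 × 0.363 × 0.637 = 0.46. Results across three groups are mixed with probability 1 − 0.363³ − 0.637³ = 0.69.

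3. *Example.* r = 0.40 has p = 0.03 and r = 0.30 has p = 0.11. On the Fisher z scale the difference is 0.424 − 0.310 = 0.114, with SE √(2/27) = 0.272, so z = 0.42 and p = 0.67.

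4. *Power of a proper comparison.* For r = 0.4 against 0, 0.424/0.272 = 1.56 gives power 0.34. Power of 80% needs about r = 0.64 against 0.

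**The case against.** **The contrast is not wrong.** Baseline as a level of time with a random subject effect is a recognised longitudinal analysis, and no passage promises baseline adjustment. This stands: part (a) is about efficiency only. It remains worth raising because the gain needs no extra data and the sample-size text itself expects a smaller effect and data loss.

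**The primary-outcome model is not clearly stated.** The mixed model is announced for behavioural, fNIRS and EEG data, and no group-by-time term is written. Applying it to DASS-21 and HADS is an inference, and the exact equality with change scores needs complete data. Both points stand. The Objective 3 contrast is nevertheless worded as a difference in changes.

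**The gain depends on assumed correlations.** It does. The rise from 60% to 74% is the favourable corner. At r = 0.8 the same selection model gives a DASS-21 ratio of 0.93 to 0.95, a gain of about 5 to 7%.

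**Part (b) is minor.** It is a supplementary analysis, regression to the mean alone is small, the 0.40-versus-0.30 case is illustrative, and an interaction test has low power. All true. But the stated purpose is individual differences in treatment response, and a within-arm correlation cannot supply that at any sample size. Low power is a reason to label the interaction exploratory.

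**Task, EEG and fNIRS outcomes have two conditions**, so a single baseline covariate is ambiguous. That is fair; a common-baseline-mean model handles them.

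**Conclusion.** Both parts hold, as improvements the plan should make.

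(a) The arm contrasts are unbiased under randomisation, provided missing data do not distort the comparison. They leave precision unused: about 7 to 27% of the variance for a DASS-21 subscale and 10 to 33% for HADS. This assumes r of 0.3 to 0.7, the selection model above, and that the stated mixed model governs these outcomes. The gain for DASS-21 is small if r is high.

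(b) The per-group correlations cannot support a statement about treatment response, whether or not sham is among the groups shown, because no between-group test is planned. This conclusion does not depend on the assumed correlations; they only indicate how easily a misleading pattern could arise.

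Confidence is medium, because the model for the primary outcomes has to be inferred.

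**What to change.** 1. For every active-versus-sham and EEG-versus-fNIRS contrast, model post and follow-up with the baseline value of the same outcome as a covariate, or use a constrained longitudinal model with a common baseline mean. The second option suits outcomes measured under two conditions.
2. State explicitly that this model applies to DASS-21 and HADS, and name the group-by-time contrasts.
3. Replace the per-group correlations with a baseline-marker-by-group interaction in that model, including sham and adjusted for baseline DASS-21. Label it exploratory, and base any statement about treatment response on the interaction estimate and its interval.

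The cost is analysis wording only, since every variable is already collected. The interaction intervals will be wide (about 34% power to separate r = 0.4 from 0 between two arms), so claims about moderators will have to be more modest.
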